### Exposure to patients with contagious pathogen infection or colonization even in the setting of PPE use can lead to pathogen contamination of HCP hands and the

**environment.** The routine care of patients placed in Contact Precautions has been noted to result in the potential for HCP colonization and the subsequent transmission of contagious pathogens. Morgan *et al* examined the frequency of contamination of HCP hands and PPE components following the performance of nonemergent care of patients colonized or infected with an MDRO. Culture growth of MDROs occurred in 1.7-4.2% of HCP hand specimens, 10.0-29.3% of glove specimens, and 2.3-12.6% of gown specimens. Overall 20.5% of HCP-patient interactions resulted in contamination of the HCP's gloves or gowns. This is concerning, as breaches in the use of this PPE could then contaminate the HCP's hands and the environment, leading to transmission to patients. The risk for contamination of PPE was significantly

increased with a HCP's duration in the room of at least 5 minutes, performance of a physical examination, and work in rooms with environmental contamination. Of equal concern, 8% of HCP room entries occurred with HCP who had colonization of a MDRO on their hands prior to room entry, emphasizing the role HCP can play in the transmission of these pathogens. While an audit for breaches in the use of PPE was not performed in this study, the frequency of PPE contamination and potential exposure risk in the event of PPE breaches is concerning. French investigators detected *C. difficile* spores on 25% of samples collected from the hands of HCP who had recently cared for a *C. difficile*-infected patient (compared to 0% in control HCP who were not exposed to *C. difficile* patients). Patient contact without the use of gloves occurred in 7.8% of observations.

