Finally, Guo *et al* examined the risk of breaches and environmental contamination with the use of three types of protective gowns and two different recommended strategies of gown removal. Contamination was assessed using a fluorescent lotion (detected by ultraviolet units) mixed with olive oil and water to mimic infectious aerosol particles. Subjects received video training on the use of PPE and, once PPE was donned, were exposed to a spray of lotion on the upper torso. PPE was then doffed in a separate area. Environmental contamination was significantly lower when using a gown removal method that pulled the gown away from the wearer during doffing. The researchers also noted that hand contamination was significantly higher among subjects who had at least 16 years of clinical experience (perhaps due to a false sense of competency with PPE use), while nurses had a higher rate of shoe contamination when compared to other provider types. A cotton gown was associated with lower contamination of the environment when compared to a water-resistant gown and a disposable plastic apron; however, undergarment contamination was increased with use of the cotton gown.

While these studies are advancements in the understanding of and risk for breaches in PPE use, there are several key limitations. First, the number of HCP studied was relatively limited, in part due to the complexities and costs of simulation assessments (Figure 2). Second, the simulation scenarios involved single patient care tasks (e.g. blood pressure assessment) rather than a more complex patient interaction than is common during patient care. Finally, the duration of the scenarios were short and may not have captured issues and risk factors associated with more prolonged PPE use.

For this study Aim, we will utilize the expertise of investigators from the Vanderbilt Center for

Experiential Learning and Assessment (CELA). Directed by [name] (an Epicenter Investigator), CELA is an advanced facility with of several interrelated programs, including human simulation using standardized patients and technical simulation utilizing state-of-the-art manikins. CELA optimizes the benefits of simulation by means of deliberate practice and multiple layers of thoughtful feedback and assessment, with a view towards enhancing professional

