## Study procedures:

Three transmissionbased precaution scenarios will be utilized (Table 2). These will involve Contact Precautions (PPE: gown and gloves), Droplet Precautions (PPE: surgical mask), and EVD-Precautions (PPE: PAPR, eve protection, hood, aown. double aloves. lea

coverings, and apron). For the Contact Precautions scenario, subjects will perform a brief history and abbreviated physical exam along with a simulated wound dressing change. For the Droplet Precautions scenario, subjects will perform a brief history and abbreviated physical examination along with management of a urinary catheter (including emptying of collection bag). For the EVD-Precautions scenario, subjects will perform a brief history and abbreviated physical exam along with medication administration through an intravenous catheter. Non-CDRT personnel will participate in both the Contact and Droplet scenarios (A-D in Table 2), while only CDRT members will participate in the EVD-Precautions scenario (E & F in Table 2). Each

scenario will have a standard 10 minute duration and a prolonged 20 minute duration (in which the exam is a standard physical exam) to assess the impact of prolonged PPE use on compliance.

Using a fluorescent compound to reproduce contaminants in assessing

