#### Study outcomes and assessment:

1) Lapses in PPE use: These will be captured via video monitoring and recording of each subject experiment from PPE donning through PPE doffing. Two independent investigators will review every scenario and note the frequency and type of breaches in the use of PPE. Investigators will be trained on a standardized method for reviewing each scenario and will use a standardized abstraction tool. The time of the lapse in relation to scenario start will be captured to examine the impact of the duration of PPE use.

2) HCP and environmental contamination: Contamination will be assessed using ultraviolet light inspection of the subjects following doffing of PPE and of the simulation room environment to assess for the number of contamination events during each scenario. The rooms will be cleaned prior to each experiment to avoid cross-contamination.

**Analysis:** A descriptive analysis of the frequency (number per minute of scenario time), number, and types of lapses in PPE use will be performed. The number of self and environmental contamination events (defined as an identified patch of fluorescent powder located in these areas) will also be described as a quantitative number and an event rate per minute of scenario time. Lapse and contamination rates will be compared between each scenario type (Contact, Droplet, and EVD), scenario duration (standard vs. prolonged), and HCP type (physician, nurse, other) using Student's t-test or Wilcoxon Rank Sum test (for duration comparison) and ANOVA or Kruskal-Wallis analysis (for precaution type and HCP type comparison given >2 study groups). For categorical outcomes (e.g. the number of lapses) Fisher's Exact Test will used for comparisons.

**Limitations:** Even with a larger study cohort, the sample size will limit the ability to examine nuanced details in patient care while wearing PPE that lead to lapses. Nonetheless, this will be one of the largest and most complex simulation experiments on PPE use published to date.

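### Aim I's prolonged scenario changes the physical exam as well as the time in PPE, so the planned duration comparison cannot be read as an effect of prolonged PPE use

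*Protocol*

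**What the plan says.** The Aim I study procedures define three precaution scenarios by their content. In the Contact scenario, "subjects will perform a brief history and abbreviated physical exam along with a simulated wound dressing change". In the Droplet scenario, "subjects will perform a brief history and abbreviated physical examination along with management of a urinary catheter". The EVD scenario has a "brief history and abbreviated physical exam along with medication administration through an intravenous catheter". All three therefore start from an abbreviated exam plus one procedural task.

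Each scenario then has a 10-minute form and "a prolonged 20 minute duration (in which the exam is a standard physical exam) to assess the impact of prolonged PPE use on compliance". Table 2 labels its two columns by duration only (A, C, E standard; B, D, F prolonged).

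The Aim I analysis paragraph compares lapse and contamination rates by precaution type, by "scenario duration (standard vs. prolonged), and HCP type (physician, nurse, other) using Student's t-test or Wilcoxon Rank Sum test (for duration comparison"). Rates are expressed per minute of scenario time, and numbers of events are also described. No term for exam content appears. The outcomes section adds that each lapse is timed from scenario start so that duration of use can be examined, and that contamination is found by ultraviolet inspection after doffing. The limitations paragraph for Aim I speaks of sample size and does not mention that exam and duration move together.

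**The concern.** The prolonged version has one stated purpose, which is to learn what longer PPE wear does to compliance. It also answers a gap the Protocol sees in earlier simulation work, whose short scenarios "may not have captured issues and risk factors associated with more prolonged PPE use". The same paragraph lists reliance on single patient-care tasks as a separate gap. Duration and complexity are thus two questions in the Protocol's own account, yet one change of script alters both.

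Exam content is a plausible rival cause. Powder is placed on the simulated patient's torso and arms as well as on the rails, the bedside table and the task site, so a fuller exam probably adds hand contact with seeded areas. The Significance section, summarising a study of contaminated gloves and gowns, names "duration in the room of at least 5 minutes, performance of a physical examination" among the factors that raised the risk.

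At stake is one of the three planned Aim I comparisons. A difference could come from the fuller exam alone. A null result could hide a wear-time effect. Neither could be recognised from the data as collected.

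**Working it through.** The Protocol gives no alpha, power or effect size for Aim I, so there is no stated figure to reproduce. The check has two parts: whether the design can separate the two factors, and what the confounding could do to each reported scale.

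**1. Identifiability.** The cells follow from the study procedures and Table 2.

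| Precaution | 10 min, abbreviated exam | 20 min, standard exam | 10 min, standard exam | 20 min, abbreviated exam |
|---|---|---|---|---|
| Contact | A | B | none | none |
| Droplet | C | D | none | none |
| EVD | E | F | none | none |

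Code a model with an intercept, two precaution terms, a duration term and an exam-type term (5 columns). Over cells A to F the duration and exam columns are identical: their correlation is 1.0 and the matrix has rank 4. The two effects are completely aliased. If duration and exam type were crossed, the same 5 columns would have rank 5 and both effects could be estimated.

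For example, an observed per-minute lapse ratio of 1.5 equals (wear effect) × (exam effect). It fits 1.0 × 1.5, 1.25 × 1.2 and 1.5 × 1.0 equally well.

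**2. Size and direction when wear time truly has no effect.** The documents do not say how much the fuller exam adds, so every input here is an assumption.

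*Assumption (a): in-use events follow hand contacts, and the fuller exam gives k = 1.5 to 2 times the contacts in total.*
- Count ratio, prolonged to standard = k = 1.5 to 2.0.
- Per-minute ratio = k × 10/20 = 0.75 to 1.0.

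*Assumption (b): the fuller exam multiplies the in-room lapse rate by m = 1 to 2, the standard in-room rate is 0.10 per minute, and each scenario also has f fixed lapses in donning and doffing.*
- Per-minute ratio = [(f + 0.10 × m × 20)/20] ÷ [(f + 0.10 × 10)/10].
- f = 0: m = 1 gives 0.10/0.10 = 1.0; m = 2 gives 0.20/0.10 = 2.0.
- f = 1: m = 1 gives 0.15/0.20 = 0.75; m = 2 gives 0.25/0.20 = 1.25.
- f = 2: m = 1 gives 0.20/0.30 = 0.67; m = 2 gives 0.30/0.30 = 1.0.

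With a nil wear-time effect, the planned rate comparison could therefore show anything from 0.67 to 2.0 under these assumptions. Dividing by minutes does not remove the confounding, and the sign of the apparent effect is not fixed.

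**3. Does the lapse time stamp rescue the comparison?** It allows early and late lapses to be compared within an encounter. But minutes elapsed follow the order of history, exam, task and doffing, and the exam differs between versions. Contamination has no time stamp at all. The look is partial for lapses and absent for contamination.

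**The case against.** The strongest reply has four parts.

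**The time stamp.** The Protocol plans to use lapse times to examine duration, and lapses are the compliance outcome. This stands to a degree. A reader might infer that no analysis of any kind can say anything about wear time; the documents do not support that for lapses. The standard-versus-prolonged contrast remains aliased.

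**The scale.** A reader might infer that the fuller exam would produce an apparent duration effect of 50% to 100%. That figure only restates an assumed contact ratio on the count scale. The plan mainly compares per-minute rates, where the same assumption gives 0.75 to 1.0, which is no increase or a decrease. No particular bias should be claimed.

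**The cited risk factors.** Both versions last more than 5 minutes and both include an exam, so the factors in the Significance section do not themselves distinguish the versions. They also concern contamination of worn PPE, not lapses or contamination found after doffing. A reader might take the passage as proof that a standard exam is riskier than an abbreviated one; it does not address that. It makes exam content a credible rival cause and no more.

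**Realism.** The Innovation section wants lengthier and more complex encounters that resemble real work, and the fuller exam serves that aim. This is legitimate, and the contrast validly describes a bundled encounter. It is not, however, the purpose the study procedures give for the prolonged version.

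A reader might also infer that a misread duration result would feed directly into the Aim II audit tool. The Aim II text says the tool will draw on breach types and the practices behind them, and does not mention the duration contrast.

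**Conclusion.** The point holds. Duration and exam content are fully aliased in all three scenario pairs, as the text of the study procedures shows directly. The planned two-group comparison cannot support a conclusion about prolonged PPE wear, whether it finds a difference or not, and the Protocol does not acknowledge this. No later analysis plan can recover the missing contrast between versions, because no cell contains it.

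The size and direction of the distortion cannot be given from the documents. The ranges above (counts 1.5 to 2.0; per-minute rates 0.75 to 1.0, or 0.67 to 2.0 under the second set of assumptions) are illustrations. The identifiability result does not depend on them.

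The fault is confined to the duration comparison. The precaution-type and HCP-type comparisons and the target of 150 subjects are not affected by it. It should be corrected, but it does not undermine Aim I as a whole.

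**What to change.** **Preferred, before the experiments start.** Keep the abbreviated exam and the wound, catheter or IV task identical in the two versions of each scenario. Fill the added 10 minutes with further history and conversation placed before the exam and task, so that the same steps and the same doffing occur after about 10 more minutes of wear. Compare lapses on those identical steps and in doffing between versions.

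*Cost:* edits to three scenario scripts, with no added subjects, staff or simulation time. The downside is less clinical complexity in the prolonged version, which the Innovation section values.

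**If the fuller exam is kept for realism.** Restrict the duration comparison of lapses to the steps common to both versions, namely the procedural task and doffing. Describe the overall contrast as a longer and fuller encounter instead of prolonged PPE use, and add the overlap of duration and exam content to the Aim I limitations.

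*Cost:* a few sentences and a restricted tabulation. This is the weaker remedy: what precedes the shared steps still differs between versions, and contamination, read once after doffing, cannot be split by step.

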#### Table 2: Simulation Scenarios for Aim I

Scenario	Standard Duration (10 mins)	Prolonged Duration (20 mins)				
Contact Precautions	Α	В				
Droplet Precautions	С	D				
EVD-Precautions	E	F				

contamination rate is effective and can be utilized for comparison with body and environmental contamination levels. A fluorescent powder (Glo Germ Co, Moab, UT) especially developed for determining hand hygiene compliance will be used in this study. The powder will be applied in standardized amounts at locations surrounding and on the simulated patient (on patient's upper torso and arms, within the simulated wound for scenarios A & B, on the urinary collection bag for scenarios C & D, on the peripheral IV hub in scenarios E & F, on both bed rails, and on the patient's bedside table) prior to the scenario start. Subjects will be blinded to the locations of powder placement.

#### Study outcomes and assessment:

1) Lapses in PPE use: These will be captured via video monitoring and recording of each subject experiment from PPE donning through PPE doffing. Two independent investigators will review every scenario and note the frequency and type of breaches in the use of PPE. Investigators will be trained on a standardized method for reviewing each scenario and will use a standardized abstraction tool. The time of the lapse in relation to scenario start will be captured to examine the impact of the duration of PPE use.

2) HCP and environmental contamination: Contamination will be assessed using ultraviolet light inspection of the subjects following doffing of PPE and of the simulation room environment to assess for the number of contamination events during each scenario. The rooms will be cleaned prior to each experiment to avoid cross-contamination.

**Analysis:** A descriptive analysis of the frequency (number per minute of scenario time), number, and types of lapses in PPE use will be performed. The number of self and environmental contamination events (defined as an identified patch of fluorescent powder located in these areas) will also be described as a quantitative number and an event rate per minute of scenario time. Lapse and contamination rates will be compared between each scenario type (Contact, Droplet, and EVD), scenario duration (standard vs. prolonged), and HCP type (physician, nurse, other) using Student's t-test or Wilcoxon Rank Sum test (for duration comparison) and ANOVA or Kruskal-Wallis analysis (for precaution type and HCP type comparison given >2 study groups). For categorical outcomes (e.g. the number of lapses) Fisher's Exact Test will used for comparisons.

**Limitations:** Even with a larger study cohort, the sample size will limit the ability to examine nuanced details in patient care while wearing PPE that lead to lapses. Nonetheless, this will be one of the largest and most complex simulation experiments on PPE use published to date.

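### Aim I compares 10- and 20-minute scenarios on events per scenario minute, although donning and doffing occur once per scenario, which biases the duration comparison towards prolonged use

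*Protocol*

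**What the plan says.** Under Study procedures for Specific Aim I, each "scenario will have a standard 10 minute duration and a prolonged 20 minute duration". The stated purpose of the longer version is "to assess the impact of prolonged PPE use on compliance". The longer version also has a standard rather than an abbreviated physical exam.

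Under Study outcomes and assessment, lapses are "captured via video monitoring and recording of each subject experiment from PPE donning through PPE doffing". Contamination of the wearer is read by "ultraviolet light inspection of the subjects following doffing of PPE"; the room is inspected as well.

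The Analysis paragraph there expresses lapses as a frequency per minute of scenario time, a number and a type. Contamination events are to be "described as a quantitative number and an event rate per minute of scenario time". The comparison follows: "Lapse and contamination rates will be compared between each scenario type (Contact, Droplet, and EVD), scenario duration (standard vs. prolonged") and HCP type. The duration contrast uses a t-test or Wilcoxon rank sum test.

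The same section also plans Fisher's exact test for the number of lapses and records when each lapse occurs relative to scenario start. It does not separate donning and doffing events from in-room events in the rate, and it does not say whether scenario time includes donning and doffing.

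**The concern.** A rate per minute is a fair scale only for events whose opportunity grows with minutes. Donning and doffing happen once per experiment, whatever its length, so lapses at those steps do not become more likely because the middle part lasts longer. The same applies to contamination picked up while removing PPE. Dividing these events by 20 instead of 10 halves their contribution to the rate.

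The fixed part is unlikely to be trivial. Aim I is explicitly about donning, use and doffing. The background sections name incorrect doffing as a route to contamination of personnel and environment, and report frequent removal errors in earlier simulation studies.

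At stake is the question for which the 20-minute version exists. A per-minute comparison can show a lower rate in the prolonged scenario when nothing about behaviour has changed, and it can absorb a real deterioration in the later minutes.

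**Working it through.** The protocol gives no event rate, effect size or power for Aim I, so there is no figure to reproduce. The check is algebra on the stated metric, with assumed values where the protocol is silent.

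**Inputs.** From the protocol: durations of 10 and 20 minutes; one donning and one doffing per experiment; rate = events per minute of scenario time. Assumed: d events per scenario tied to donning and doffing; r in-room events per minute, equal in both versions (no true duration effect); scenario time = the nominal 10 or 20 minutes.

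**Rate and ratio.**
- Rate over T minutes = (d + rT)/T = r + d/T.
- Ratio, 20 to 10 minutes = (r + d/20)/(r + d/10).
- With s = d/(d + 10r), the donning/doffing share of events in the 10-minute version, this equals 1 − s/2.

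| s | Ratio with no true duration effect |
|---|---|
| 0% | 1.00 |
| 25% | 0.875 |
| 50% | 0.75 |
| 75% | 0.625 |
| 100% | 0.50 |

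**Illustrative values of d and r (assumed).**

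| d | r = 0.1 | r = 0.2 |
|---|---|---|
| 1 | 0.15/0.20 = 0.75 | 0.25/0.30 = 0.83 |
| 2 | 0.20/0.30 = 0.67 | 0.30/0.40 = 0.75 |
| 3 | 0.25/0.40 = 0.63 | 0.35/0.50 = 0.70 |

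The range is 0.63 to 0.83.

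**How much real harm can be hidden.** Let the in-room rate be r in minutes 1–10 and r′ in minutes 11–20. The two scenario rates are equal when (d + 10r + 10r′)/20 = (d + 10r)/10, so r′ = r + d/10 and r′/r = 1/(1 − s). The in-room rate after minute 10 must be 1.33 times the earlier rate (s = 25%), 2 times (50%) or 4 times (75%) before the comparison even shows equality.

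**Chance of a misleading significant result.** Poisson simulation, no true duration effect, s = 50%, independent experiments, two-sided 0.05. The table gives the proportion of runs significant in favour of the prolonged version. Event totals and numbers per duration are assumed.

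| Events per 10-minute scenario | Experiments per duration | t-test | Wilcoxon |
|---|---|---|---|
| 2 | 30 | 36% | 28% |
| 2 | 75 | 75% | 58% |
| 4 | 30 | 64% | 50% |
| 4 | 75 | 96% | 92% |

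With s = 0 the t-test figure is 2.0% to 2.5%, as it should be on one side.

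**If scenario time includes donning and doffing.** With an assumed 5 minutes for both, the denominators are 15 and 25 and the ratio is (15/25)(2 − s) = 1.2 − 0.6s. That is 0.90 at s = 50% and 1.05 at s = 25%. The bias is smaller and changes direction below s = 1/3.

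**With the components separated.** Donning and doffing events per scenario: d/d = 1.00. In-room events per in-room minute: r/r = 1.00. Both hold for every s.

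**The case against.** The strongest reply is that the protocol does not rest on the rate alone. Counts are described beside rates, Fisher's exact test is named for the number of lapses, and lapse times are recorded for the express purpose of examining duration of use. A reader would see a higher count next to a lower rate. This stands as mitigation: the information needed for a sound answer will exist. It does not repair the rate comparison, which is the one given the t-test or Wilcoxon test for duration. Nor does the protocol say which result governs if count and rate disagree.

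A second reply is that scenario time is undefined and might include donning and doffing. This also stands, and it limits what can be claimed about size and, at low s, direction.

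A third reply is that such detail belongs in a statistical analysis plan. Here, however, the protocol itself fixes the metric and the tests.

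Three stronger readings are tempting but not supported:
- A reader might infer that the prolonged scenario is bound to look safer. It is not: a large enough rise in the in-room rate after minute 10 would offset the bias, and the denominator is undefined.
- A reader might infer that the total lapse count per scenario is the right primary contrast. It carries the opposite artefact, because in-room exposure doubles and the exam is fuller. With 4 events per 10-minute scenario, half of them fixed (d = 2, r = 0.2), the count rises from 4 to 6 with no change in behaviour, while the rate falls from 0.40 to 0.30 per minute.
- A reader might infer that the Aim II audit tool would inherit a wrong result. The Aim II section on tool development draws on types of breach and the practices behind them, with expert review and pilot observation, not on the 10- versus 20-minute ratio.

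**Conclusion.** The concern holds as a bias in the stated duration comparison of rates. If scenario time is the nominal 10 or 20 minutes and the in-room rate is constant, any donning or doffing events in the numerator push the 20-to-10-minute ratio below 1. It lies between 1.00 and 0.50 depending on s, and between 0.63 and 0.83 for the illustrative d and r above. The direction favours prolonged use, and a real rise in in-room lapses can be masked.

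The size is not known, because the protocol gives neither s nor a definition of scenario time. The simulated error rates rest on assumed event totals and numbers per duration and on independence between experiments; they show that the bias can matter, not how often it will. For contamination the argument applies to whatever part arises at doffing. Contamination acquired during care, including patches in the room, can accumulate with time, and the protocol plans no time record for it that would separate the two.

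**What to change.** For the duration comparison in Aim I:

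1. Define scenario time as in-room time, excluding donning and doffing.
2. Analyse donning lapses and doffing lapses as counts per scenario, with no time denominator.
3. Analyse in-room lapses per in-room minute, using the recorded lapse times. Add a comparison of minutes 1–10 with minutes 11–20 within the prolonged scenario, which addresses prolonged wear most directly.
4. Compare post-doffing contamination per scenario, stating that the longer version also brings more in-room exposure and a fuller exam, so a difference cannot be put down to wear time alone.
5. Do not make the total lapse count per scenario the primary duration contrast.

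The cost is slightly more analysis and fewer events in each component, hence less precision for each. No new data are needed: the video already runs from donning to doffing, and lapse types and times are already to be abstracted.
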